1.3 SCHEDULE OF ACTIVITIES (SOA)

Table 2: Schedule of Activities

	Screening	Treatment Period 1				Washout Period		Treatment Period 2				
Study Visit	Visit 0	Visit 1	Visit 2	Visit 3	Visit 4	Telephone Follow-up	Washout	Visit 5	Visit 6	Visit 7	Visit 8	Telephone Follow-up
Day	-28 to -1	0A	3A	5A	7A	7±1 after Period 1	8-28	0B	3B	5B	7B	7±1 after Period 2
Time after CSII insertion [h]			72±3	120±3	168±3				72±3	120±3	168±3	
Procedures	Screening	Rand. / Insertion/ Clamp	Clamp	Clamp	Clamp	Phone call	Routine	Enrollment/ Insertion/ Clamp	Clamp	Clamp	Clamp	Phone call
Example Day of Week		Fri	Mon	Wed	Fri			Fri	Mon	Wed	Fri	
Labs/Questionnaires/Instructions												
Informed consent	X											
Demographics	X											
Medical history	X											
Urine Pregnancy test ¹	X	X						X				
Physical exam (incl. height/weight) ²	X							X				
Concomitant medication review	X	X	X	X	X	X		X	X	X	X	
CBC	X											X
HbA1c	X											
C-Peptide	X											
Basic Metabolic Panel	X											
ECG	X											
Vital signs ³	X	X	X	X	X			X	X	X	X	
Randomization		X										
Patient Instructions ⁴	X	X	X	X	X	X		X	X	X	X	
Adverse event review and evaluation ⁵	X	X	X	X	X	X		X	X	X	X	
Device Applications/Removals												
Download Pump and SMBG Data	X	X	X	X	X			X	X	X	X	
Insert CGM sensor	X	X						X				
Review CGM data	X	X	X	X	X				X	X	X	
Remove Participant's infusion set (AM of clamp procedure), insert CSII catheter (abdomen)		X						X				

Remove CSII catheter (& insert patient's routine CSII set)					X ⁶						X ⁶	
--	--	--	--	--	----------------	--	--	--	--	--	----------------	--

Clamp											
Switch pump to 0.1 U/h at when IV insulin is started (evening before clamp procedure)		X	X	X	X				X	X	X
Insert 2 IV cannulas for insulin and dextrose infusion (evening before clamp procedure)		X						X			
Prime tubing with insulin and connect to CSII infusion set and then prime cannula		X						X			
PK/PD study (run-in, bolus, clamp)		X	X	X	X			X	X	X	X
Venous sample BG/serum insulin ⁷		X	X	X	X			X	X	X	X
Patient meal (at end of clamp procedure) ⁸		X	X	X	X			X	X	X	X
Others											
Evaluate insertion site ⁹		X	X	X	X	X		X	X	X	X
Video insertion		X						X			
Record CGM and CSII performance issues		X	X	X	X			X	X	X	X

¹ Pregnancy test required for all female participants of child-bearing age without documented menopausal status or removal of key organs.

² Only the Visit 1 body weight value will be used to calculate insulin doses and infusion rates for both treatment periods

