2.3 RISK/BENEFIT ASSESSMENT

2.3.1 POTENTIAL RISKS

A list of known disease, treatment, CSII sets, glucose pump and CGM product risks and potential risks are listed below. A list of anticipated adverse events and study definitions can be found in Section 8.3 of this protocol. There may be other risks that are unknown at this time and new risks that may be identified during the study.

Fingerstick

- Fingerstick BG tests may produce pain and/or bruising at the test site.

Diabetes Disease Risks

- Hypoglycemia and associated symptoms such as sweating, trembling, difficulty thinking and dizziness
- Hyperglycemia
- Diabetic ketoacidosis
- Coma
- Death

Insulin pump Use/Therapy

- Slight bruising at the site of insertion (common)
- Slight discomfort at the time of insertion of the insulin delivery cannula (common)
- Bleeding at insertion site (rare)

- Clinically significant infection or inflammation at the site of insertion (very rare), due to the extended cannula wear time this risk might be slightly higher but is considered to occur only rarely.
- Allergy to insulin (very rare)

Note: Participants will be instructed to regularly check the insertion site for any skin reactions. Skin reactions shall be noted in the provided diary and the study team shall be contacted via the helpline.

Commercial CSII Catheter Insertion Site Reactions

- Reddening
- Induration
- Purulence
- Itching
- Other non-specified skin irritation

Venipuncture and IV catheter insertion

- Localized infection – an infection in the tissue around the site
- Phlebitis – inflammation of the wall of the vein
- Hematoma – an accumulation of blood within the tissues that clots to form a solid swelling
- Fatigue caused by transient anemia due to frequent blood draws (insulin and glucose concentration determination)
- Thrombus formation and necessary insertion of a new IV catheter

Continuous Glucose Monitoring Risks

- Trivial discomfort at the time of insertion of CGM (common)
- Slight bruising at the site of insertion (unlikely)
- Bleeding at insertion site (rare)
- Infection at the site of insertion (rare)

Humalog (insulin lispro injection, USP [rDNA origin]) for injection (ID: 3273563)

- Allergy
- Anaphylaxis
- Antibody Production
- Hypokalemia
- Lipodystrophy
- Peripheral Edema
- Renal or Hepatic Impairment
- Weight gain

Glucose Clamp Related Risks

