Risks of glucose clamp testing are similar to those during routine therapy and include periods of hypoglycemia requiring BG adjustments. Since participant BG levels will be monitored constantly during the glucose clamp study period, it is not anticipated that participants will experience any further risks as compared to routine insulin pump use and monitoring.

Participants enrolled in this study are adults who have had type 1 diabetes for at least 12 months and at least 6 months of experience with insulin pump therapy. These criteria were set to minimize risk. Additionally, screening assessments will be applied to exclude patients with anemia or known cardiovascular disease who may be at greater risk of procedure-induced anemia or whose hypoglycemia symptoms may be masked by concomitant medication. (See section 5 for inclusion and exclusion criteria.)

Potential risks associated with Achilles infusion set use and/or extended wear include but are not limited to the following:

Infusion Site Reactions

- Localized pain
- Bleeding
- Bruising
- Induration
- Infection
- Itching/ Pruritus
- Purulence
- Reddening (erythema)
- Swelling
- Other
- Non-specified irritation

Infusion Set Issues

- Infusion Set Failure
- Infusion Pump Failure
- Infusion pump dosing error

Achilles Device Related Risks

- Cannula Kinking
- Insulin leak from site
- Insulin leak from set or tubing
- Adhesive failure
- Cannula dislodgement

- Cannula insertion failure (not all holes below epidermis)
- Incomplete tubing prime
- Incomplete cannula prime
- Air Bubbles in tubing
- Defective venting in insulin pump / reservoir / infusion set connection

A list of anticipated adverse events (AEs) and study specific definitions can be found in Cap Bio Study 150 -004 Feasibility Study Anticipated Adverse Event Definition List, V2. 060619 (Protocol Attachment A). There may be other risks that are unknown at this time and new risks that may be identified during the study.

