4.2 SCIENTIFIC RATIONALE FOR STUDY DESIGN

This study is designed as a cross-over study to allow each participant to serve as their own control in effort to address intra-participant variability associated with insulin absorption, glucose lowering effect and cannula tolerability. This study will enroll up to 30 CSII-experienced adults with T1DM. An active control of insulin delivery using a commercialized CSII set will be used since administration of a placebo is infeasible. To minimize bias of a sequence effect, the sequence of treatment assignment will be randomized. Furthermore, a washout period that is equal to a minimum of five half-lives of rapid acting insulin will be required in order to eliminate any treatment effect between treatment periods and to allow the study participants to recover from blood loss associated with clamp procedures.

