5.3 EXCLUSION CRITERIA

An individual who meets any of the following criteria will be excluded from participation in this study:

- 1) Participants whose average total daily insulin dose exceeds 85 units/day (i.e. typically change insulin reservoirs more often than every 4 days on average)
- 2) Participants who routinely change their commercial insulin infusion sets on average less often than every 4.5 days¹
- 3) Female participant is pregnant or nursing²
- 4) Participant has abnormal skin at intended device infusion sites (existing infection, inflammation, burns, or other extensive scarring)
- 5) Participant has hemoglobin <12.0 g/dL or potassium < 3.5 mEq/L at screening

¹ This will be determined during screening by evaluating the data downloaded from the patient's Medtronic pump. The pump data includes date and time of "cannula prime" events which can be used as surrogate for infusion set change time.

² Documented negative pregnancy test results for female participants required unless participant is menopausal without any spontaneous menstrual cycles for >12 months or key organs have been removed.

- 6) Participant has documented history in last 6 months of severe hypoglycemia associated with cognitive dysfunction sufficiently severe to require third party intervention or a history of impaired awareness of hypoglycemia.
- 7) Participant has a history of diabetic ketoacidosis in the last 6 months
- 8) Participant has known cardiovascular disease considered to be clinically relevant by the investigator
- 9) Participant has known arrhythmias considered to be clinically relevant by the investigator
- 10) Participant has known history of:
 - a) Cushing's Disease,
 - b) pancreatic islet cell tumor, or
 - c) insulinoma
- 11) Participant has:
 - a) Lipodystrophy,
 - b) extensive lipohypertrophy, as assessed by the investigator
- 12) Participant is undergoing current treatment with:
 - a) Systemic oral or intravenous corticosteroids,
 - b) monoamine oxidase (MAO) inhibitors,
 - c) non-selective systemic beta-blockers,
 - d) growth hormone,
 - e) thyroid hormones, unless use has been stable during the past 3 months
 - f) SGLT2 inhibitors
- 13) Participant has significant history of any of the following, that in the opinion of the investigator would compromise the participant's safety or successful study participation:
 - a) Alcoholism,
 - b) drug abuse

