5.6 SCREEN FAILURES

Patients who fail screening due to hemoglobin <12.0 g/dL and potassium < 3.5 mEq/L eligibility criteria may be rescreened 1 time up to 2 weeks later.

The site may rescreen one time for A1C >8.5% and/or C-peptide. ≥ 0.6 nmol/L up to 2 weeks after the participant screen failure.

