6.1.1.2 SCREENING AND BASELINE (DAY -21 TO DAY -1, VISIT 0)

Participants will be screened and tested to verify study eligibility criteria including a physical exam, complete medical history and laboratory testing. Female participants of child-bearing age, who do not have a documented history of menopause (defined as at least 12 months without menses and/or removal of key organs) must undergo a urine pregnancy test within 7 days of the planned intervention date. All participants must also undergo a urine drug/alcohol screen test, complete blood and metabolic panels within the required screening period (Table 5).

- Patients who fail screening due to hemoglobin <12.0 g/dL and potassium <3.5 mEq/L eligibility criteria may be rescreened for study eligibility 1 time up to 2 weeks later.
- Patients who fail the drug/alcohol screening test may be rescreened for study eligibility one (1) time up to 2 weeks later.

If participants are not currently using and/or are not familiar with the Dexcom G6® CGM sensor, study staff will insert the study sensor during the screening visit and are asked to familiarize themselves with the sensor for 7 days. After one week, CGM data will be downloaded and assessed. If CGM data shows readings for approximately 80% of sensor wear time, the participant may be enrolled in the study. If readings are less than 80%, the participant will be given another week of training. If after the second training period, the threshold of 80% is still not met, the participant is not eligible to participate in the trial.

Participants will be provided with diabetes diaries and a bag of material (see 6.1.1.8) for times spent at home in between study visits to the CRU. Participants will be reminded to fast 12 hours prior to Visit 1 and to avoid a high-carb dinner (e.g. pizza). They are furthermore instructed to refrain from strenuous exercise and alcohol during the 24 hours preceding Visit 1.

Table 5: Screening and Baseline Required Exams

Requirement	Comments
Inclusion criteria	Ensure patients meets all of the inclusion and none of the exclusion criteria
Informed consent	Written consent required by participant
Demographics	Age, gender, race, ethnicity
Medical history	All co-morbidities, prior interventions, Indication for Treatment
Urine Pregnancy test	Female participants of child-bearing potential who are not documented post-menopausal or have undergone extirpation of key organs

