8.2 SAFETY AND OTHER ASSESSMENTS

The following labs and procedures will be conducted to ensure patient safety:

- **Physical examination** (e.g., height and weight, organ systems, motor or vision assessment, or other functional abilities). If appropriate, discuss what constitutes a targeted physical examination.
- **Vital signs** (e.g., temperature, pulse, respirations, blood pressure while seated). Carefully consider which vital signs (if any) should be measured to ensure that only essential data are collected. Include any specific instructions with respect to the collection and interpretation of vital signs.

- **Biological specimen collection and laboratory evaluations.** Urine pregnancy test, CBC to exclude anemic conditions, C-Peptide tests to confirm T1 diabetes and rule out T2 diabetes, and HbA1c levels at screening. Electrocardiogram to evaluate cardiac status. Frequent BG measurements to titrate D20% IV administration rate and keep patients in euglycemia range.
- **Special assays or procedures required.** Multiple plasma samples will be frozen and stored to measure insulin levels via radioimmunoassay (RIA)
- **Counseling procedures, including any dietary or activity considerations:** Patients will be trained on study procedures and will be asked to maintain their usual diet and exercise regimens during the course of the entire study. Prior to clamp visits, however, they are asked to refrain from strenuous exercise and eating meals high in carbohydrates.
- **Assessment of study intervention adherence:** a CGM device will be applied to identify any hyperglycemia or hypoglycemia.
- **Administration of questionnaires or other instruments** will be utilized to collect pain scores (VAS) and maintain AE records (phone visit and diary during washout period). Additionally, usability questionnaires will collect patient and clinician perspective on product usability to identify sources of user error.
- **Assessment of adverse events.** Reported AEs and SAEs will be reviewed by the investigator or designee and Medical Monitor.

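### Minor safety improvement: no hemoglobin is scheduled between screening and the Period 2 clamps, although the washout is relied on for recovery from up to 240 mL of blood loss

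*Protocol*

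**What the plan says.** Protocol section 4.2 justifies the washout by the need to remove any treatment effect and "to allow the study participants to recover from blood loss associated with clamp procedures". Its minimum length is expressed in insulin half-lives. The synopsis sets it at 7 to 21 days.

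Section 2.3.1 lists "Fatigue caused by transient anemia due to frequent blood draws" among the risks. The safeguard it names is at entry: "screening assessments will be applied to exclude patients with anemia or known cardiovascular disease who may be at greater risk of procedure-induced anemia". Exclusion criterion 5 in section 5.3 reads "Participant has hemoglobin <12.0 g/dL or potassium < 3.5 mEq/L at screening". Section 6.1.1.2 asks for "complete blood and metabolic panels within the required screening period", and section 8.2 lists "CBC to exclude anemic conditions" in a sentence that closes on screening.

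Table 2 (section 1.3) marks the CBC at Visit 0 and once more in its last column, the telephone contact headed "7±1 after Period 2". The physical exam and the urine pregnancy test are repeated at Visit 5; the CBC is not. The check on the evening before each clamp (section 5.4) covers strenuous exercise and any medical condition that the investigator thinks could interfere, with no hemoglobin.

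Section 6.1.1.5 puts the maximum draw at 62.0 mL per clamp and 248 mL per week, and says that both weeks together stay below one unit (525 mL).

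**The concern.** The recovery that the washout is meant to provide is assumed rather than checked before up to four more clamps. A participant admitted at or just above 12.0 g/dL could start Period 2 below the protocol's own entry limit without anyone knowing. Section 7.2 lets the investigator withdraw a participant for a laboratory abnormality, but before Period 2 no scheduled hemoglobin exists for that ground to act on.

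**Working it through.** **1. Where a hemoglobin value could come from.** The CBC row of Table 2 has 12 visit cells, with marks in cells 1 and 12. The vital-signs row falls correctly on Visits 0–4 and 5–8, so the columns appear to align and cell 12 is the call after Period 2. There are three possible readings:
- As printed: a telephone call, where blood cannot be drawn.
- A slip from Visit 8, the adjacent column: the value comes at the last clamp visit.
- A slip from Visit 5 (cell 8, four columns away): this alone would close the gap, and no text supports it.

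**2. Blood volume per clamp.** The expression in section 6.1.1.5 is 24 × 1.5 + 6 × 1.0 + 36 × 0.5 = 36 + 6 + 18 = 60.0 mL, so the stated 62.0 mL does not reproduce. The Table 6 volumes give the same answer: 7.5 + 2.5 + 4.5 + 1.5 + 6.5 + 13.5 + 4.5 + 8.0 + 11.5 = 60.0 mL, over 15 + 5 + 3 + 1 + 7 + 9 + 3 + 10 + 13 = 66 samples.
- Per period: 4 × 60 = 240 mL (stated 248).
- Both periods: 8 × 60 = 480 mL (the stated figure implies 8 × 62 = 496). Both are below 525 mL.

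**3. Why 240 mL is a ceiling.** A period ends when the set is changed out (section 6.1.1.8; Table 2, footnote 6). Section 9.4.1 assumes 40–50% failures. I read that as the share of sets failing before the day 7 clamp, and assume that the day 0 clamp is always done. Then 50–60% of periods reach 240 mL, and the mean per period is:
- all failures before the day 3 clamp: (1 + 3 × 0.5) × 60 = 150 mL, or (1 + 3 × 0.6) × 60 = 168 mL;
- all failures after the day 5 clamp: 3.5 × 60 = 210 mL, or 3.6 × 60 = 216 mL.

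**4. Age of the screening value at Visit 5, after a full first wear period.** The minimum is 1 + 7 + 7 = 15 days. The maximum is 28 + 7 + 21 = 56 days, or 21 + 7 + 21 = 49 days if the Day -21 heading of section 6.1.1.2 governs.

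**5. Size of the hemoglobin fall.** Assumption not in the documents: blood volume (BV) of 60–75 mL/kg. At the 70 kg used as an example in section 4.3, BV is 4200–5250 mL. With continuous dilution and no recovery, Hb = 12.0 × exp(−loss/BV).

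| Loss | BV 4200 mL | BV 5250 mL | Fall from 12.0 g/dL |
|---|---|---|---|
| 60 mL (one clamp) | 11.83 | 11.86 | 0.1–0.2 |
| 240 mL (four clamps) | 11.33 | 11.46 | 0.5–0.7 |
| 480 mL (eight clamps) | 10.70 | 10.95 | 1.0–1.3 |

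These are upper bounds, because recovery over 7–21 days is set to zero. How much is regained is what the test would show.

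**The case against.** The strongest case against is that the risk is small and already managed. The protocol describes it only as fatigue from transient anemia. It sets an entry floor of 12.0 g/dL, caps the volume below one unit, uses a double-stopcock technique to save blood, and allows a washout. It also has a call after Period 1, a physical exam at Visit 5, vital signs every 2 hours during clamps, adverse event review and the evening check in section 5.4. Nothing in the documents requires a hemoglobin before Period 2, and section 4.2 states a rationale, not an entry condition. Most of this stands, and it keeps the point minor. What it does not answer is that none of these safeguards yields a hemoglobin value.

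Readers might infer more than the documents support:
- *That participants face a material risk of anemia.* The fall before recovery is about 0.5–0.7 g/dL at most after four clamps, and many periods will end before four.
- *That the protocol plans an impossible blood draw.* The CBC is the only mark in the last column, so a slip from Visit 8, by the author or in reading the PDF, is plausible. The point holds on either reading.
- *That the end-of-study CBC should simply be moved into the washout.* That would remove the check at the highest cumulative loss, up to 480 mL.
- *That the volume slip undermines the safety statement.* It overstates the loss, and the total is below 525 mL on either figure.
- *That the SAP omits hemoglobin altogether.* Sections 4.3.3 and 4.4.5 name ECG and vital signs but no CBC; the attached list of tables is not available to settle it.

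**Conclusion.** The gap is real and the point is minor. On neither the printed reading of Table 2 nor the likely Visit 8 reading is there a hemoglobin between screening and the Period 2 clamps, although recovery from blood loss is one of the two stated reasons for the washout. By Visit 5 the screening value may be 15 to 56 days old. The ceiling on loss is 240 mL per period. The matching fall of about 0.5–0.7 g/dL rests on the assumed 60–75 mL/kg at 70 kg, a start at 12.0 g/dL and no recovery. It matters mainly for participants who enter near the limit. The corrected volumes of 60.0, 240 and 480 mL change no conclusion. The sponsor stopped the study after the seventh completer (SAP section 2.5), so the design change applies to a restart or follow-on clamp study.

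**What to change.** For any restart or follow-on study:
- **Add a hemoglobin/CBC at the evening admission before Visit 5**, when the IV lines are placed anyway (section 6.1.1.4). If same-night results are not available, draw it at an earlier in-person contact.
- **Have the investigator review it before the first Period 2 clamp.** Use 12.0 g/dL as a reference for the section 7.2 judgement, not as an automatic stop.
- **Allow one recheck within the 7–21 day washout**, in line with section 5.6, under which a screening failure "may be rescreened 1 time up to 2 weeks later". This needs Visit 5 to be planned early enough: a test around day 14 leaves 21 − 14 = 7 days, and one around day 7 leaves 14 days.
- **Keep the end-of-study CBC, but mark it at Visit 8** instead of the telephone call.
- **Correct section 6.1.1.5 and Table 6** to 60.0 mL per clamp, 240 mL per period and 480 mL in total. The comparison with one unit stands.

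For the terminated study, any post-baseline hemoglobin that was drawn could be listed with its date relative to the clamps.

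The cost is one small extra tube and edits to Table 2 and the text; a separate visit is needed only if results cannot be had the same night. A low value may delay a participant near the limit or lose that participant for Period 2. Missing the 2±1 week window is a withdrawal reason, and treated participants are not replaced (section 7.2).

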4.3 JUSTIFICATION FOR DOSE

A bolus of commercial U-100 insulin lispro (0.15 units/kg) will be infused through an investigational or commercial infusion set into the SC tissue of the abdomen at time zero (t0 on DOI and on Days 3,5 and 7) of each glucose clamp PK/PD study using a Medtronic pump. The concentration of BG will be maintained approximately in the 95±15 mg/dL range using an IV infusion of 20% dextrose and/or insulin infusion.. The IV dose may range from 0.1 to 3.0 units/h depending on the patient's regular basal rate.

This insulin lispro bolus dose (0.15 units/kg) is slightly higher than a typical dose used to cover an average sized meal for a T1DM patient with an average insulin/carbohydrate ratio

(0.15 units/kg x 70 kg = 10.5 units). The majority of the published PK/PD studies utilized a 0.15 unit/kg bolus dose, some used a 0.20 units/kg bolus dose, and a few studies used a 0.10 or 0.12 unit/kg dose.

Insulin lispro will be infused through the same investigational or commercial insulin infusion set after each glucose clamp (or until CSII failure) using a Medtronic insulin pump and a basal/bolus pattern of delivery. The basal infusion rate, meal bolus dose and correction dose will be adjusted by each study patient according to their routine clinical methods [SMBG glucose measurements, CGM glucose measurement (if available), insulin to carbohydrate ratio, meal size and meal composition]. Study participants requiring a large daily insulin dose may require a change out of their pump reservoir with fresh insulin as needed during each treatment period.

